4.1 Study Design Summary

4.1.1 Overall Design

This is a Phase 3, multicenter, randomized, double-blind, placebo-controlled study of CVC for the treatment of Stage 2 or 3 liver fibrosis in adult subjects with NASH. The study will be conducted in 2 parts: Part 1 (histopathological surrogate endpoint) and Part 2 (clinical outcomes).

In Part 1, approximately 1200 subjects will be randomized 2:1 to receive CVC or placebo to assess the effect of CVC on the histopathological surrogate endpoint at Month 12. Subjects continuing beyond Month 12 will remain in the same treatment arm throughout the end of the study.

Part 2 of the study will focus on assessing the effect of CVC on clinical outcomes and will include approximately 2000 subjects, of which approximately 1200 subjects will have been randomized in Part 1.

The study population will include adult subjects with a liver biopsy diagnosis of NASH and Stage 2 or 3 liver fibrosis (by NASH CRN system) as confirmed by an independent central pathologist. CVC and placebo will be administered as double-blinded study drug. Study drug (CVC or placebo) must be taken once daily with food. A Data and Safety Monitoring Board (DSMB) will be formed to review ongoing data from Part 1 and Part 2 of this study.

The study will be terminated when adjudicated events have been accrued in approximately 367 unique subjects across Part 1 and Part 2. All subjects will have an End of Study visit at that time and will return to the clinic for a Follow-up visit 30 days after the last dose of study drug.

Subjects who permanently discontinue study drug before planned end of study are encouraged to complete all subsequent study visits and participate (without treatment) in Part 2 of the study for assessment of clinical outcomes (at the discretion of the investigator, subjects who permanently discontinue study drug may be followed every 6 months unless otherwise specified by the protocol). Subjects who undergo early termination from the study will return to the clinic within 48 hours for an early discontinuation visit and will return to the clinic for a Follow-up visit 30 days after the last dose of study drug.

Survival data will be collected for all study subjects at the end of the study.

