
Multiple imputation (Part 2: primary efficacy endpoint)
	
Treatment Period
	
Informative Censoring Imputation Model:⁶
 
Let k index the censoring times before t^*. (Note: $t^* \approx 96$ months for subjects randomized in Part 1 and 84 months newly randomized subjects in Part 2.)
 
Let $t_{k,0}$ denote the latest failure time prior to c_k (or equal to it) when $t_1 \leq c_k$.
 
Let $t_{k,j}$ denote the jth failure time after c_k, $j = 1, 2, \dots, J_k$, when $c_k < t_M$. Note that the possible values of J_k range from 1 to M, depending on the position of c_k with respect to the order of the t_m's ($m = 1, 2, \dots, M$): J_k equals M if $c_k < t_1$, and J_k equals 1 if $t_{M-1} = c_k < t_M$. From the observed data, we obtain the Kaplan–Meier estimates $\hat{S}(t)$ for the survival distribution for the event times, and it has support on the observed event times (t_1, t_2, \dots, t_M).
 
The estimate for the conditional cumulative incidence function for a subject with early discontinuation at c_k to have the event by the time t in $[t_{k,j} < t < t_{k,j+1}]$, for $j = 1, 2, 3, \dots, J_k$ with $t_{k,J_k+1} = t^*$ can be obtained as follows.
 $\hat{F}_{j,k}(\theta) = 1 - \frac{\hat{S}(t_{k,j+1})^\theta}{\hat{S}(c_k)^\theta}$ 
The estimate for the conditional probability for a subject with early discontinuation at c_k to have the event by the time t in $[c_k < t < t^*]$, can be obtained as follows.
 $\hat{f}_{j,k}(\theta) = \frac{\hat{S}(c_k)^\theta - \hat{S}(t^*)^\theta}{\hat{S}(c_k)^\theta}$ 
Under this formulation, $\theta > 1$ (or < 1) implies a higher (or lower) hazard after c_k for patients with premature discontinuation at c_k than for patients with continued follow-up after c_k. The test treatment group would usually have $\theta_{\text{active}} > \theta_{\text{placebo}}$ specified, and with $\theta_{\text{placebo}} = 1$, $\theta = (\theta_{\text{active}} / \theta_{\text{placebo}}) = \theta_{\text{active}}$ becomes a single parameter for calibrating sensitivity analyses. The value of θ_{active} will be finalized before database lock.
 
*** To obtain the survival function estimates $\hat{S}(t_{k,j+1})$ and $\hat{S}(c_k)$ to generate $\hat{f}_{j,k}(\theta)$ and $\hat{F}_{j,k}(\theta)$:
 <pre>proc lifetest data=xxx OUTSURV=SURVEST; time AVAL*CNSR(1); strata ARMCD / test=logrank; SURVIVAL CONFTYPE=LINEAR; run;</pre> 
In SURVEST datasets, SURVIVAL column is what we need to obtain the survival function estimates. Please note that $\hat{F}_{j,k}(\theta)$ is from 0 to 1. The multiple imputation scheme is as follows:
 
 1. Generate a random number p from the uniform distribution between 0 and 1, and for computational convenience, use linear interpolation to impute failure times.

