
Parameter type	Timing	Missing Data Handling
		
Use UNIFORM function in SAS to generate a pseudorandom number p from the uniform distribution on $[0, 1]$ for the following scenario.
 
 2. Suppose a subject has early discontinuation at time c_k, perform the following failure time imputation: 
 a. If $0 \leq p \leq \hat{F}_{k,0}(\theta)$, then impute the failure time $t_k^{(l)}$ between c_k and $t_{k,1}$ as $c_k + (t_{k,1} - c_k) \frac{p}{\hat{F}_{k,0}(\theta)}$, where l indicates the lth imputation set. b. If $\hat{F}_{k,j}(\theta) \leq p \leq \hat{F}_{k,j+1}(\theta)$, for $j = 0, 1, 2, 3, \dots, (J_k - 1)$, then impute failure time $t_k^{(l)}$ between $t_{k,j+1}$ and $t_{k,j+2}$ as $\left(t_{k,j+1} + (t_{k,j+2} - t_{k,j+1}) * \frac{p - \hat{F}_{k,j}(\theta)}{\hat{F}_{k,j+1}(\theta) - \hat{F}_{k,j}(\theta)} \right)$, where $t_{k,J_k+1} = t^*$. c. If $p > \hat{F}_{k,J_k}(\theta)$, then manage the patient as having no event by the end of follow-up time t^*. 3. Suppose a patient has premature discontinuation between t_M and t^*, so that $(t_M < c_k < t^*)$: 
 a. If $p \leq \hat{f}_{j,k}(\theta)$, then impute failure time $t_k^{(l)}$ between c_k and t^* as $c_k + (t^* - c_k) \frac{p}{\hat{f}_{k,0}(\theta)}$; b. Otherwise, manage the patient as having no event by the end of follow-up time t^*. 
The imputation is performed separately for the patients with premature discontinuation in each treatment group.
 
The above imputation procedure is repeated to form L imputed data sets.
 
*** Combining Chi-square distributed statistics after multiple imputation: After multiple imputation, it is possible to combine the test results from all available tests in PROC LIFETEST such as log-rank test. Each of these tests is based on a chi-square distributed statistic that can be normalized using a Wilson-Hilferty transformation. If X^2 is chi-square distributed with d degrees of freedom, then
 $W = \sqrt[3]{\frac{X^2}{d}} \approx N\left(1 - \frac{2}{9d}, \frac{2}{9d}\right), \text{ or}$ $\frac{\sqrt[3]{X^2/d} - \left(1 - \frac{2}{9d}\right)}{\sqrt{\frac{2}{9d}}} \approx N(0,1)$ 
Test statistics and their corresponding degrees of freedom can be found in the ODS output dataset HomTests produced by PROC LIFETEST when using the STRATA statement with TEST option. These test

Parameter type	Timing	Missing Data Handling

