The sample size for the primary endpoint analysis in Part 2 is based on the estimated event-free survival rate of 80% for the placebo group and detection of a hazard ratio of 0.62 by the anticipated end of the study at Month 60 (corresponding to a median event-free survival time of approximately 15 years for placebo and 25 years for CVC). A total of 2000 subjects (2:1 randomization ratio between CVC and placebo) enrolled approximately uniformly over 2 years for an overall study duration of approximately 8 years (2 years of accrual period plus 5 to 6 years of follow-up) will lead to about 367 events, after accounting for an overall dropout rate of 20%. With these events, there will be 85% power to demonstrate strong evidence of superiority of CVC over placebo (at a 2-sided 0.00125 significance level, for a single registration study), and 99% power to test the superiority of CVC over placebo (at the 2-sided test 0.05 significance level for a registration study).

EAST 6.4 is used for the calculation.

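### The Part 2 informative-censoring imputation runs to a cohort-wide horizon that lies past nearly every subject's own end of study; the effect on this sensitivity analysis is small

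*SAP*

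**What the plan says.** SAP section 5.1.1.1.5, Table 5-4 (multiple imputation, Part 2 primary endpoint), sets one approximate horizon per cohort: "96$ months for subjects randomized in Part 1 and 84 months newly randomized subjects in Part 2". If a subject's random draw yields no event, the rule is to "then manage the patient as having no event by the end of follow-up time" t*.

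On who is imputed, the model opens with "Let k index the censoring times before" t*. The formulas and steps that follow speak of early or premature discontinuation, and the scheme closes with: "The imputation is performed separately for the patients with premature discontinuation in each treatment group".

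After a subject leaves, the hazard is multiplied by θ. Placebo has θ = 1. The SAP says the active arm would usually have the larger value, which "will be finalized before database lock".

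The end of the trial is defined differently. SAP section 4.1.1: "The study will be terminated when adjudicated events have been accrued in approximately 367 unique subjects across Part 1 and Part 2". SAP section 5.1.2 plans 2000 subjects entering roughly uniformly, with an "overall study duration of approximately 8 years (2 years of accrual period plus 5 to 6 years of follow-up". Time to event runs from each subject's Baseline date (Table 5-13), and subjects without an event are censored at the last recorded visit (Table 5-14).

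**The concern.** With one calendar end and staggered entry, the longest follow-up a subject can have is the study end minus that subject's entry date. A horizon common to a whole cohort ignores this. A subject who drops out may be given an event at a time when the trial would already have ended had that subject stayed. Subjects with no imputed event are held at risk past that point too.

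A missing-not-at-random analysis should charge only for follow-up lost to withdrawal. When θ for CVC exceeds 1, the extra months carry the raised hazard in the CVC arm only, so the result leans against CVC for time that was never missing. A tipping-point value of θ would then read slightly too low.

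The opening wording adds a second problem. Event-free completers are also censored before t*, so nothing in the definition of t* separates a completer from a dropout.

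**Working it through.** **1. Reproduce the plan (SAP 5.1.2).** Inputs: placebo 80% event-free at Month 60, HR 0.62, 2:1 allocation, 2000 subjects, 24-month uniform accrual, 96 months in total, 20% dropout.

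- Placebo hazard: −ln(0.80)/60 = 0.003719 per month, median 15.5 years. CVC hazard: 0.62 × 0.003719 = 0.002306, median 25.1 years. The plan says about 15 and 25.
- Power with 367 events (Schoenfeld): √(367 × 2/9) × |ln 0.62| = 9.031 × 0.478 = 4.317. Subtracting 3.227 gives 86.2% at two-sided 0.00125. Subtracting 1.960 gives 99.1% at 0.05. The plan says 85% and 99%.
- Expected events per subject: λ/(λ+γ) × [1 − mean of exp(−(λ+γ)u)], with u uniform on 72 to 96 months and γ = 0.00301 (20% observed dropouts). Placebo: 0.2383 × 666.7 = 158.9. CVC: 0.1560 × 1333.3 = 208.0. The total of 366.9 matches the planned 367.

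The inputs therefore imply a study end near month 96.

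**2. Own end of follow-up against t\*.** Accrual is 2000/24 = 83.3 subjects per month, and own end = 96 − entry month.

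| Part 1 size | Cohort | Entry (months) | Own end (months) | t* | Excess (months), mean |
|---|---|---|---|---|---|
| 1200 (planned) | Part 1 | 0 to 14.4 | 81.6 to 96 | 96 | 0 to 14.4, mean 7.2 |
| 1200 | New in Part 2 | 14.4 to 24 | 72 to 81.6 | 84 | 2.4 to 12, mean 7.2 |
| 1293 (SAP 5.2.1) | Part 1 | 0 to 15.5 | 80.5 to 96 | 96 | 0 to 15.5, mean 7.8 |
| 1293 | New in Part 2 | 15.5 to 24 | 72 to 80.5 | 84 | 3.5 to 12, mean 7.8 |

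On this schedule no newly randomised subject can reach 84 months.

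**3. Effect on the result.** I simulated 200 trials of 2000 subjects with exponential times, about 20% observed dropout and study end at month 96. Each had 20 imputations from arm-specific Kaplan-Meier curves, as the SAP specifies. Cox log hazard ratios were pooled by Rubin's rules; the SAP's pooling of log-rank statistics was not run. Only premature discontinuations are imputed. θ is not given, so a range is shown. Without imputation the HR is 0.616.

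| θ for CVC | HR, own end | HR, SAP t* | Difference | Imputed events (SAP t*) | Of these, past own end (CVC) |
|---|---|---|---|---|---|
| 1 | 0.6151 | 0.6155 | 0.0004 | 53.7 | 6.9 (4.1) |
| 1.5 | 0.6490 | 0.6535 | 0.0045 | 67.3 | 8.6 (5.7) |
| 2 | 0.6813 | 0.6899 | 0.0086 | 80.2 | 10.1 (7.3) |
| 3 | 0.7400 | 0.7561 | 0.0161 | 103.3 | 12.6 (9.8) |
| 5 | 0.8406 | 0.8682 | 0.0276 | 140.5 | 16.0 (13.2) |

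Other Kaplan-Meier runs at 8 years and θ = 2 gave 0.670 to 0.675, 0.673 to 0.681, 0.653 to 0.662 and 0.673 to 0.684. The rise is thus about 0.005 to 0.011.

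For scale, moving θ from 1 to 2 with own ends shifts the HR by 0.6813 − 0.6151 = 0.066, so the horizon adds 0.0086/0.066, or about 13% of that. The tipping point moves little: 0.6899 is reached at θ = 2 under the SAP's t*. By linear interpolation it is reached at 2 + (0.6899 − 0.6813)/(0.7400 − 0.6813) = 2.15 with own ends. The share of trials with p < 0.00125 at θ = 2 was 61.5% against 65.5%; each share has a standard error of about 3 points.

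**4. If completers were imputed too.** At 8 years and θ = 2 the HR would be about 0.71 to 0.72, a larger move than the horizon itself causes.

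**The case against.** The best defence has four parts. The horizons are marked approximate. The closing scope sentence, both imputation steps and the explanation of θ confine imputation to early or premature discontinuation. Beyond the last observed event the Kaplan-Meier curve is flat, so no event can be imputed there. And this is one of several sensitivity analyses, where a shift against CVC is conservative. All of that stands and limits the size. It does not make the horizon right: nothing in the SAP ties t* to a subject's own end date.

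A reader might infer more, and four stronger readings do not hold.

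- *The rule penalises CVC in general.* Both arms are imputed to t*. At θ = 1 the HR does not move, and the SAP has not yet fixed θ.
- *Completers are imputed.* The opening phrase introduces notation, and the operative sentences limit the scope to discontinuations. The wording needs aligning; it does not establish the wider analysis.
- *The overshoot is about 20 months.* That needs a study end at 7 years (7.8 + 12 = 19.8). On the plan's inputs only about 317 to 329 events would have accrued by then, so a trial that stops at about 367 would still be running. If events accrue slowly the study runs longer and the overshoot shrinks or reverses.
- *A robust result would be reported as fragile.* A rise of about 0.01 in the HR at θ = 2 does not support that.

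**Conclusion.** Wrong as written, small effect, sensitivity analysis only. On the planned schedule t* lies past nearly every subject's own end, by 7 to 8 months on average, so the stated rule imputes some events that the trial could not have observed. When θ for CVC exceeds 1 this moves the result modestly against CVC: about 0.005 to 0.011 in the HR at θ = 2, with about 10 imputed events past own end.

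The shift grows with θ and with an earlier study end. At 7 years and θ = 2, Kaplan-Meier runs gave 0.654 to 0.668 and 0.674 to 0.690. The primary log-rank test does not use t* and is unaffected.

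These sizes assume exponential event times, constant dropout, uniform accrual, the plan's HR and event rate, and illustrative values of θ. The actual end date is event-driven, so the real excess may be larger or smaller.

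**What to change.** In SAP Table 5-4 (multiple imputation, Part 2 primary endpoint):

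1. Define t* for each subject as the Part 2 end-of-study (data cut-off) date minus that subject's Baseline date, in place of 96 and 84 months.
2. Let c_k index only subjects who left follow-up without an event before that date. Identify them from the disposition record, because a completer's last visit may fall somewhat before the cut-off.
3. State that subjects event-free at the end of study stay censored at their last visit and are not imputed.

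The cost is a few sentences and one derived date per subject, with no new data. The SAP already has to settle θ before database lock, so these changes can be made in the same revision.

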### 5.3.3. Phase 2b Study in Subjects with NASH and Liver Fibrosis

The Phase 2b study (CENTAUR; Study 652-2-203) was a randomized, double-blind, placebo-controlled, multinational, 2-year study. The study was designed to determine the efficacy and safety of CVC for the treatment of NASH in adult subjects with liver fibrosis. The study population included subjects with a nonalcoholic fatty liver disease activity score (NAS)  $\geq 4$  and liver fibrosis Stage 1 to 3 based on the NASH Clinical Research Network (CRN) criteria who were at increased risk of disease progression due to the presence of T2DM, body mass index (BMI)  $> 25$  kg/m^2 and meeting at least 1 of the criteria for metabolic syndrome, or bridging fibrosis (NASH CRN Stage 3) and/or definite NASH (NAS  $\geq 5$ ). Subjects were randomized in a 2:1:1 ratio to receive 1 of 3 treatments as follows:

- CVC 150 mg once daily for 2 years (Arm A; CVC/CVC group)
- Placebo once daily for 1 year followed by CVC 150 mg once daily for an additional 1 year (Arm B; placebo/CVC group)
- Placebo once daily for 2 years (Arm C; placebo/placebo group)

Fibrosis stage, NASH status, and NAS were assessed in serial liver biopsies read by an independent central pathologist at baseline, Year 1, and Year 2. The independent central pathologist remained blinded to individual subject treatment assignment throughout the conduct of the study.

A total of 289 subjects (intent-to-treat [ITT] population) were randomized into the CENTAUR study. Overall, 39 of 289 subjects (13.5%) withdrew early during Year 1 (Treatment Period 1), with the most commonly reported reasons for early discontinuation during Year 1 being due to AEs and withdrawal of consent. A total of 250 subjects (86.5%) completed Year 1, and 242 subjects (83.7%) entered Year 2 (Treatment Period 2). During

Year 2, 16 subjects (5.5%) withdrew early, with the most commonly reported reason for early discontinuation during Year 2 being due to AEs, which were more commonly reported in the CVC/CVC group (3.4%, 5 subjects) compared with the placebo/CVC group (1.4%, 1 subject) and the placebo/placebo group (0 subjects).

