		
statistics obtained from each imputed dataset can be normalized using the above formula and the normalized values can let be input for PROC MIANALYZE in order to obtain combined results for these chi-square based tests.
 <pre> DATA _tmc_tests1; set _tmc_tests; *** ChiSq is a chi-square distributed statistic (e.g., logrank) and DF is its corresponding degrees of freedom as produced by PROC LIFETEST ***; ChiSq_wh=((ChiSq/DF)**(1/3) - (1-2/(9*DF)))/SQRT(2/(9*DF)); ChiSq_stderr_wh = 1.0; run; proc sort data=_tmc_tests1; BY _Imputation_; run; proc MIANALYZE data=_tmc_tests1; modeleffects ChiSq_wh; stderr ChiSq_stderr_wh; ods output parameterestimates=resprefix._tests; run; *** Combining results of Cox regression and exponentiation of the combined log-hazard ratios: Cox regression model parameter estimates from PROC PHREG represent log hazard ratios. They are normally distributed and do not need any further transformation to be combined with Rubin's rules using PROC MIANALYZE. However, the end results need to be exponentiated to obtain the numerical values of the hazard ratios and associated confidence intervals. proc phreg data=_tmc_1; by _Imputation_; class trtvar <classvars>; model timevar * censvar(censval) = trtvar covars / risklimits ties=efron rl; ods output ParameterEstimates=_es; run; /* Combine model coefficients. */ proc sort data=_es; by Parameter ClassVal0 _Imputation_; run; proc MIANALYZE data=_es; by Parameter ClassVal0; modeleffects Estimate; stderr stderr; ods output ParameterEstimates = _es_mianal; run; /*Exponentiate in order to obtain hazard ratio estimates and confidence intervals */ data resprefix. hr; </pre>

Parameter type	Timing	Missing Data Handling
		<pre>set_es_mianal; Log_HR_comb=Estimate; HR_comb=exp(Estimate); HR_LCL_comb=exp(LCLMean); HR_UCL_comb=exp(UCLMean); keep Parameter ClassVal0 Log_HR_comb HR_comb HR_LCL_comb HR_UCL_comb Probt; rename Probt=HR_pval_comb; run;</pre>

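### The Part 2 informative-censoring imputation holds one Kaplan-Meier curve per arm fixed in every imputed data set, so the pooled log hazard ratio gets a standard error that is slightly too small.

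*SAP*

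**What the plan says.** SAP Table 5-4 (Section 5.1.1.1.5) sets out the informative-censoring model for the Part 2 primary endpoint. Table 5-14 lists it as sensitivity analysis 2.

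- **Curve.** "From the observed data, we obtain the Kaplan–Meier estimates" is where the model starts. The code is one PROC LIFETEST call with "strata ARMCD / test=logrank", without resampling and without processing by imputation number. The conditional event probabilities, with theta as exponent, are built from that output.
- **Random step.** Step 1 reads "Generate a random number p from the uniform distribution between 0 and 1". The remaining steps turn p into an event time or a censored time.
- **By arm.** "The imputation is performed separately for the patients with premature discontinuation in each treatment group".
- **Repetition.** "The above imputation procedure is repeated to form L imputed data sets". L is given no value.
- **Pooling.** The Cox log hazard ratios "do not need any further transformation to be combined with Rubin's rules using PROC MIANALYZE". The log-rank chi-squares are pooled after a Wilson-Hilferty transformation.

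Theta for CVC is to be fixed before database lock. Neither document describes a bootstrap, a posterior draw or any other redraw of the curve.

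**The concern.** Rubin's total variance adds a between-imputation part to the average within-imputation variance. That is valid only if the imputed sets differ for two reasons: chance in each subject's outcome, and uncertainty about the model the outcomes are drawn from. Here only the first is present, because rerunning PROC LIFETEST on the same observed data returns the same curve. The Part 1 imputation in the same table does not share the gap, since PROC MI's logistic method redraws its coefficients in each imputation.

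At stake is the confidence interval of the analysis meant to show how far the Part 2 hazard ratio depends on what happened to subjects who left. The shortfall runs in one direction. It grows with dropout and with theta, the two conditions this analysis exists to examine.

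**Working it through.** **Step 1: reproduce the plan's own figures.** SAP Section 5.1.2 gives 367 events, hazard ratio 0.62, 2:1 allocation, 80% event-free on placebo at Month 60 and 20% dropout.

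- Schoenfeld: √(367 × 2/3 × 1/3) × |ln 0.62| = 9.031 × 0.4780 = 4.317.
- At two-sided 0.00125, Φ(4.317 − 3.227) = 86.2% (SAP: 85%). At 0.05, Φ(4.317 − 1.960) = 99.1% (SAP: 99%).
- With constant hazards, the medians are 15.5 and 25.1 years (SAP: about 15 and 25).

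The SAP gives no figure for the pooled standard error, so that part needs simulation.

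**Step 2: simulate the SAP procedure.**

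- From the SAP: 1334 vs 666 subjects, the hazards above, and uniform accrual over 2 years. Follow-up is 72 to 96 months, from the 8-year study duration.
- Assumed: exponential times, dropout unrelated to outcome, L = 50, theta 1, 1.5 or 2 for CVC and 1 for placebo, and an unstratified Cox model. There were 5000 trials per dropout setting.

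The lower dropout setting left 17.9% of subjects dropped out and 372 events on average, close to the plan. The higher one left 36.0%. The fixed curve (SAP as written) was compared with a curve re-estimated from a within-arm bootstrap sample in each imputation.

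Rubin variance: T = W + (1 + 1/L)B. Example at 18%, theta 1: fixed, 0.00990 + 1.02 × 0.00100 = 0.01092, SE 0.1045; redrawn, 0.00990 + 1.02 × 0.00115 = 0.01107, SE 0.1052.

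| Dropped out | Theta | B fixed / redrawn | SE fixed / redrawn | SE ÷ empirical SD, fixed | Coverage, fixed | SE ÷ empirical SD, redrawn |
|---|---|---|---|---|---|---|
| 18% | 1 | 0.00100 / 0.00115 | 0.1045 / 0.1052 | 0.991 | 94.9% | 0.996 |
| 18% | 1.5 | 0.00110 / 0.00132 | 0.1041 / 0.1051 | 0.986 | 94.8% | 0.996 |
| 18% | 2 | 0.00117 / 0.00145 | 0.1036 / 0.1050 | 0.982 | 94.6% | 0.994 |
| 36% | 1 | 0.00209 / 0.00295 | 0.1096 / 0.1135 | 0.965 | 94.4% | 0.998 |
| 36% | 1.5 | 0.00222 / 0.00333 | 0.1085 / 0.1136 | 0.951 | 94.0% | 0.996 |
| 36% | 2 | 0.00228 / 0.00358 | 0.1074 / 0.1134 | 0.939 | 93.4% | 0.992 |

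Coverage is of the estimator's own long-run mean by the nominal 95% interval. Relative to the redrawn version, the SE is 0.7-1.3% low at 18% and 3.4-5.3% low at 36%. The mean pooled log hazard ratio hardly differs (at 18%, theta 2: −0.3866 fixed, −0.3868 redrawn), so the estimate is not biased by the fixed curve.

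**Step 3: separate check with no treatment effect, theta 1.** Fixed vs redrawn SE: 0.0962 vs 0.0968 at 20% dropout (0.6% low) and 0.1010 vs 0.1045 at 40% (3.3% low).

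**Step 4: is 36-40% a reasonable stress case?** Protocol Section 5.3.3 reports that in Phase 2b "39 of 289 subjects (13.5%) withdrew early during Year 1", and that 16 of the 242 who entered Year 2 then withdrew (6.6%), leaving 226. Carrying the Year 2 rate to Year 7 gives 1 − (226/289) × (226/242)^5 = 1 − 0.782 × 0.710, or about 44%.

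**The case against.** The strongest case against is size. At the planned dropout the interval still covers 94.6-94.9% of the time, and no conclusion would turn on an SE 1-2% low. That stands, and it is why the point is minor. The larger figures need about twice the planned dropout, and retention may be better than in Phase 2b: Protocol Section 7.1 encourages subjects who stop study drug to stay in follow-up, and survival data are collected for everyone at study end.

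The method also rests on a cited paper that cannot be consulted here and may contain a redraw step. If so, the SAP's steps and code still leave it out.

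Three stronger readings are tempting and not supported.

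- **Inflated error rate.** A reader might infer that the 0.00125 or 0.05 level is compromised. Those levels attach to the primary stratified log-rank test (SAP Sections 5.1.1.3.1 and 5.1.1.3.3). This is one sensitivity analysis among several, with no alpha and no decision rule.
- **Pooled log-rank p-value too small.** As coded for Part 2, it is conservative for a separate reason. With 1 degree of freedom the transformed statistic cannot fall below −(7/9)/√(2/9) = −1.65, so the lower tail of the two-sided PROC MIANALYZE p-value is never reached. Simulated as coded under no effect (theta 1), it fell below 0.05 in about 2.9% of trials at 20% dropout and 3.8% at 40%; a second run gave about 2.4-3.5%. It would be too small (about 5.8% and 6.6%) only if the one-sided step that appears in the Part 1 code were added.
- **Dropout above 50%.** Spreading the Phase 2b withdrawals (39 + 16 of 289 in 2 years) at a constant rate gives about 52% by Year 7, and a larger shortfall. The reported rate fell between Year 1 and Year 2, so a constant rate is not what the Protocol shows.

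**Conclusion.** The concern holds, with minor severity. As written, the Part 2 imputation leaves out the sampling uncertainty of the Kaplan-Meier curves, so the Rubin standard error and confidence interval of the pooled log hazard ratio in sensitivity analysis 2 are too small. The understatement is about 1-2% near the planned 20% dropout and about 3-6% at 36-40%, with the upper end of each range at theta above 1.

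The direction follows from the text alone. The sizes rest on the simulation assumptions listed above, with L and theta chosen because the SAP leaves both open. The primary analysis, its alpha and the point estimate are unaffected.

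**What to change.** In Table 5-4, add a step before step 1: in each imputation, draw a bootstrap sample of subjects with replacement within each arm, re-estimate the survival curve from that sample, and impute the original subjects who discontinued from the redrawn curve. Pool with Rubin's rules as now. State the value of L; this can be settled together with theta, which the SAP already has to finalize before lock.

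The cost is one SAP sentence, a few lines of SAS and L extra PROC LIFETEST runs. The interval widens slightly. In the simulations the redraw brought the SE to within about 1% of the empirical SD in every setting. No data collection or primary analysis changes.
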